8.2 Subject Enrollment

Enrollment of the subject will occur after the subject is screened for eligibility, informed of the study requirements and the subject signs the informed consent.

When a subject and the principal investigator or authorized designee, as required, have personally signed and dated the IC, the subject is considered a subject enrolled in the study. The date the subject signed the IC and data protection authorization if applicable must be documented in the subject's medical records.

Subjects will be recruited from the practices and clinics of the participating Study Investigators or from other non-investigator Otolaryngologist or Rhinologist physician referrals. Potential subjects will have

Medtronic Business Restricted

the need to undergo nasal/sinus surgery using a space-occupying stent. Subjects may continue their medical therapy regimen (antibiotics, steroids, nasal sprays, etc) per their treating physician.

All subjects will be screened for study eligibility. A qualified member of the investigational site's research team will review the inclusion and exclusion criteria to screen each subject.

There will be no minimum number of subjects enrolled at a site, no site will enroll greater than 60% (45 subjects) of the total enrollment goal. This numerical goal is to ensure a diversity of experience and surgical techniques throughout the study, while allowing flexibility of enrollment based on eligible populations of subjects.

Subjects will be considered enrolled into the study when they have:

- Been informed of the study design, objectives, risks and benefits
- Met the eligibility criteria
- Confirmed interest in participation by signing a written Informed Consent and Research Authorization Form

8.3 Inclusion Criteria

- Subject is at least 18 years of age.
- Subject has the need to undergo nasal/sinus surgery with the intended need for nasal sinus packing (i.e., Novapak).
- After being informed of the nature of the study; the subject understands, agrees to its provisions, is willing to participate and provide written consent.
- Mentally stable and able to follow the instructions for self-assessment/questionnaire completion.

8.4 Exclusion Criteria

- Subject has a shellfish allergy.
- Subject has known bleeding disorder or prescribed anticoagulants.
- Subject has craniofacial abnormalities that may interfere with access to the sinuses.
- Subject is immunocompromised (e.g., taking immunosuppressive medication).
- Subject is participating in another investigational device, biologic, or drug study and has not completed the primary endpoint(s) or if there is a potential for clinical interference beyond the primary endpoint.

9. Study Procedures

The subjects will encounter the following procedures during their participation in the study:

- Lund-MacKay Scores (pre-surgical history)
- Lund-Kennedy Score (pre-surgery, 14, 30)
- SNOT-22 questionnaire (pre-surgery, 14, 30)

Medtronic Business Restricted

- Endoscopic Exams (day 0, 14, 30)
- Functional Endoscopic Sinus Surgery (day 0)
- Insertion of the Novapak device in the nasal cavity (day 0)
- Post – Surgical Daily saline irrigations (day 1 through day 14 + longer if prescribed by physician)
- Debridement of adhesions at day 14 and/or day 30 (if necessary)
- Removal of residual product at day 14 (if necessary)

A patient needing sinus surgery with the use of dissolvable packing would encounter all or most of these procedures during the course of treatment.

9.1 Schedule of Events

Table 4: Planned Visits, Procedural Events and Data Collection

Visit	Procedure	Data Collection
Pre-Surgery	Inform subject about the study requirements Ask shellfish allergy questions Schedule Surgery	Consent document signed SNOT-22 (subject)
Day 0	Endoscopic exam	Lund-MacKay Scores Lund-Kennedy Scores (baseline)
	Functional Endoscopic Sinus Surgery Other interventions if bleeding more than minimal	Procedural Details Boezaart Surgical Field Grading Scale (pre-packing) Boezaart Surgical Field Grading Scale (post-packing) Question: Bleeding controlled post packing? Collect Adverse Events and/or Device Deficiencies
Day 1, 2, 3...	Daily Irrigations	Subject records volume / date Subject records any Adverse Events
Day 14 (-2, +5)	Office Visit Endoscopic exam Observe for residual product (remove) Debride Adhesions (if necessary) Review Subject Irrigations Records	SNOT-22 (subject) Lund-Kennedy Scores Question: residual product? Score Adhesions (Valentine method) Question: Bleeding controlled? Collect Adverse Events and/or Device Deficiencies
Day 30 (-2, +12)	Office Visit Endoscopic exam Debride Adhesions (if necessary)	SNOT-22 (subject) Lund-Kennedy Scores

Medtronic Business Restricted

	Review Subject Irrigations Records	Score Adhesions (Valentine method) Collect Adverse Events and/or Device Deficiencies
--	------------------------------------	---

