4.1.2 Secondary Objective(s)

The secondary objectives of this study will gather data to support the effectiveness of Novapak's inherent features and claims of performance:

Adhesions – Sinus packing devices act as a space occupying stent to prevent raw tissues from contact and forming unwanted, obstructive tissue connections known as synechia or adhesions. This study will collect the number of adhesions observed by endoscopic examination as well as a grade of the adhesions based on the percentage of vertical height of the middle turbinate taken up by the adhesion. This data will be compared to historical data related to adhesions post sinus surgery.

Control of bleeding – Sinus packing devices control bleeding by absorption and pressure on the bleeding surfaces known as the tamponade effect. Chitosan a component of Novapak also has hemostatic properties. This study will collect data related to post-operative bleeding. Since bleeding can be different for each subject and based on the extent of tissue trauma; a baseline observation immediately post-surgery using the Boezaart Surgical Field Grading Scale will be collected. After the packing is applied the surgical field will be graded again. In addition, any residual bleeding will be observed and noted at the subject visits.

Aid in healing – Novapak acts as an adjunct to aid in the natural healing process by providing a moist environment for the tissues during the proliferation phase of wound healing. In addition, the chitosan component within Novapak has hemostatic properties and is antibacterial to reduce unwanted microbial action which could lead to inflammation. The physician will grade the sinuses before surgery and then at each subject visit using the Lund-Kennedy scoring system. In addition, the subjects will provide sinus health responses to the SNOT-22 questionnaire prior to surgery and again at each subject visit.

Novapak is a dissolvable sinus packing device that under normal use with daily irrigation will be eliminated from the sinuses without the need for removal from the physician. An observation of residual Novapak will be done by the physician at each subject visit. These observations will be compared to the subject's compliance to daily irrigation.

5. Study Design

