9.8 Surgical Procedure

On the day of the Sinus Surgical Procedure the subject should be scheduled giving enough time for study procedures and data collection prior to surgical procedures.

The following information is required to be collected at the surgical procedure visit:

- Lund-Mackay Scores (pre-surgical history)
- Subject completes the baseline SNOT-22 questionnaire
- Physician conducts Endoscopic Examination pre-surgery and grades the sinuses using Lund Kennedy Scores
- Surgical Information: Date of surgery, the surgical location (left, right or both nasal cavities), type of surgery (e.g. turbinectomy, septoplasty, FESS, etc.)
- Collect any Adverse Events and/or device deficiencies
- Physician grades bleeding post-surgery and before packing is inserted using the Boezaart Surgical Field Grading Scale
- Physician grades bleeding post-surgery and after packing is inserted using the Boezaart Surgical Field Grading Scale
- The type of Novapak used and lot number(s)

Subjects may be treated with the Novapak device unilaterally or bilaterally, the number of devices used could be one or two per subject. Therefore, total product used in this study would be a minimum of 75 if a single device is used, to approximately 150 if two devices are used per subject. Note: Physicians are free to modify the size and shape of the device to fit in a unique individual anatomy.

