9.13 Assessment of Efficacy

The following parameters will be used to assess the effectiveness of the Novapak device used according to device indications:

Adhesions – in order to show that Novapak acts a nasal stent to separate tissue or structures compromised by surgical trauma and separate and prevent adhesions between mucosal surfaces in the nasal cavity the study physician will count the number of adhesions present and grade the sinuses using the ordinal scale method published by Valentine 2010.

Control of bleeding – in order to show that Novapak controls minimal bleeding the study physician will grade the bleeding post-surgery and prior to packing using the Boezaart Surgical Field Grading Scale. After inserting the Novapak product with irrigation to hydrate the product the bleeding will be graded again using the same scale.

During the day 14 visit the physician will be asked if any bleeding is observed during the exam and prior to any debridement procedure.

Progression of healing – The Lund Kennedy endoscopic grading system will be used to show that Novapak acts as an adjunct to aid in the natural healing process. The physician will perform an endoscopic exam prior to surgery (to establish a baseline), at day 14 and day 30 visits (to show progressive healing).

Residual Novapak – Novapak dissolves naturally with daily irrigation. Any residual Novapak in the nasal cavity will be recorded at the 14 day visit and compared to the subject compliance to the daily irrigation log.

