# Novapak Prospective Observational Clinical Trial Form Statistical Analysis Plan

Version 1.0

Page 7 of 7

- The graded percentage of vertical height of the middle turbinate taken up by the adhesion using an ordinal scale (0-3) from procedure through 1-month post treatment.
- The measure control of bleeding by comparing Boezaart Surgical Field Grading Scale scores post operatively, prior to Novapak insertion and post Novapak insertion.
- The measure of healing by comparing Lund-Kennedy scores before surgery and at 2 weeks and 1-month post treatment.
- The measure of health by comparing subject scores from the SNOT-22 questionnaire before surgery and at 2 weeks and 1-month post treatment.

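### Other Day 0 haemostatic interventions are neither timed against the two Boezaart grades nor handled in the SAP, so the pre/post change may overstate Novapak's effect; SAP 7.9.2 also lists no analysis of the two bleeding questions

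*Protocol*

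**What the plan says.** **Other interventions.** The Day 0 surgery row of Protocol Table 4 (Section 9.1, repeated in the synopsis) includes "Other interventions if bleeding more than minimal". The data column of that row holds procedural details, both Boezaart grades, the item "Question: Bleeding controlled post packing", and adverse events and device deficiencies.

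**The two grades.** Section 9.8 fixes the first: "Physician grades bleeding post-surgery and before packing is inserted using the Boezaart Surgical Field Grading Scale". Section 9.13 fixes the second: "After inserting the Novapak product with irrigation to hydrate the product the bleeding will be graded again using the same scale". Section 9.13 gives the purpose of the comparison as "in order to show that Novapak controls minimal bleeding".

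**Required surgical data.** Section 9.8 lists "Surgical Information: Date of surgery, the surgical location (left, right or both nasal cavities), type of surgery", along with the grades, the Novapak type and the lot number. Other haemostatic measures are not named.

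**Analysis.** SAP 7.9.2 evaluates bleeding control by comparing Boezaart scores "post operatively, prior to Novapak insertion and post Novapak insertion". SAP 7.1.3 takes in every eligible patient who used the device. No rule covers subjects who had another intervention.

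**Bleeding questions.** Besides the Day 0 item, Table 4 asks at Day 14 whether bleeding is controlled. Sections 9.9 and 9.13 have the physician note any bleeding at that examination. Protocol 4.1.2 and SAP 4.2 both state that "any residual bleeding will be observed and noted at the subject visits". SAP 7.9.2 lists neither question, and the Day 30 lists in Table 4 and Section 9.9 contain no bleeding item.

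**The concern.** The study has one arm, so the only thing that ties the Boezaart change to Novapak is that nothing else acting on bleeding happens between the two grades. The plan permits something else on the same day and does not place it in time. If a subject's bleeding is stopped by another measure after the first grade and before the second, the whole fall is attributed to packing, and that fall may be among the largest in the data.

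The situation is foreseeable. Protocol 10.1 says that bleeding with packing in place may need sutures, cautery or additional packing. Of the seven field complaints it lists (1 + 3 + 1 + 2), three are post-operative bleeding that needed secondary control. Protocol 5.2 says the data will support the labelling claim on control of minimal bleeding, and Protocol 3.2 places the study behind a CE Mark submission.

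The two bleeding questions are the plan's direct record of whether bleeding was controlled. Without a listed analysis, the bleeding part of the effectiveness objective rests on the Boezaart comparison alone.

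**Working it through.** The plan has no figure to reproduce. Protocol 13.5 and SAP 6 state that the minimum of 75 subjects was not derived statistically, and no expected bleeding rate, effect size or SD is given. The check is therefore one of timing, followed by an illustration.

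**Step 1: effect of timing on the Boezaart change**

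| Other intervention given | Effect on the pre/post change |
|---|---|
| Before the pre-packing grade | Already in the baseline; no inflation, and it may leave less room to improve |
| Between the grades | Its effect is added to Novapak's |
| After the post-packing grade | None |
| Not used | None |

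Only the second row biases the comparison, and the documents do not say which row applies.

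**Step 2: size if it falls between the grades**

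Let c be the mean fall without the other intervention, f the share of subjects who have one between the grades, and d the extra fall it produces in them. Then

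observed mean fall = c + f × d, so bias = f × d.

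Both f and d are assumptions.

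| f | d = 1 grade | d = 2 grades |
|---|---|---|
| 0% | 0 | 0 |
| 5% | 0.05 | 0.10 |
| 10% | 0.10 | 0.20 |
| 20% | 0.20 | 0.40 |
| 30% | 0.30 | 0.60 |

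The SAP does not say that the comparison will be of means, and the grade is ordinal. In a shift table the equivalent statement is that a share f of subjects is misattributed.

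**Step 3: the Day 0 question**

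Take n = 75 and let k be the number recorded as controlled who had another intervention after the pre-packing grade. Control without such an intervention is (recorded controlled − k) / 75, with Clopper-Pearson 95% limits. Two starting points are assumed: all 75 recorded as controlled, or 68.

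| k (share) | Start at 75/75 | Start at 68/75 |
|---|---|---|
| 0 | 100% (95.2–100) | 90.7% (81.7–96.2) |
| 4 (about 5%) | 71/75 = 94.7% (86.9–98.5) | 64/75 = 85.3% (75.3–92.4) |
| 8 (about 10%) | 67/75 = 89.3% (80.1–95.3) | 60/75 = 80.0% (69.2–88.4) |
| 15 (20%) | 60/75 = 80.0% (69.2–88.4) | 53/75 = 70.7% (59.0–80.6) |
| 22 (about 30%) | 53/75 = 70.7% (59.0–80.6) | 46/75 = 61.3% (49.4–72.4) |

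The Day 0 answer can be affected by the same interventions as the grades. Adding that question to the SAP without recording the interventions would therefore not settle attribution.

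**Step 4: objective against analysis list**

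SAP 4.2 includes residual bleeding at visits in the objective, but SAP 7.9.2 has no matching analysis. Both documents speak of the subject visits, yet only the Day 14 visit has a bleeding item.

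**The case against.** The text can be read in a harmless way. Table 4 lists other interventions straight after the surgery and names none after packing. Section 9.13 runs from grade to insertion and hydration to second grade, with nothing in between. Since the device is indicated for minimal bleeding, heavier bleeding might naturally be dealt with as part of surgery, before the baseline grade. That reading is plausible, but neither document states it, and under it the bias is zero.

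Capture may already exist. The procedural-details item and the Application CRF could record these measures, and the CRFs are not in the documents. Treatment of an adverse event must also be reported (Section 11.1), although mild bleeding within five days of surgery is exempt from reporting unless it worsens. Even full capture would leave the SAP without a rule.

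On the omitted questions, Protocol 13.1 says collected data will be used as appropriate and categorical variables summarised, and SAP 3 allows an addendum. Mild bleeding at Day 30 would fall outside the five-day exemption and be reportable as an adverse event. These points make the omission a gap in the analysis list. It is still a gap, because SAP 7.9.2 is where the effectiveness analyses are set out.

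A reader might also infer that every subject given an extra measure is a device failure. The documents do not support that. The trigger is bleeding beyond minimal, which exceeds the stated indication, and Section 10.1 attributes bleeding to inadequate packing or to excessive bleeding. Making control by packing alone the main result could therefore count against the device unfairly.

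Finally, the endpoint is secondary, descriptive and unpowered, which limits how much weight the point carries.

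**Conclusion.** The point stands as a gap in attribution. Other Day 0 interventions are permitted, are not timed against the two grades, are not named in the required data, and have no handling rule in the SAP. The Boezaart change may overstate Novapak's effect if any of them falls between the grades. On assumed values (5–30% of subjects, 1–2 extra grades) the inflation of a mean change is 0.05 to 0.6 grade. It is zero if the interventions precede the first grade, follow the second, or are not used. Frequency and timing are not in the documents, so no point in that range can be called likely.

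Two stronger readings are tempting. One is that Novapak is credited with every other intervention, so that bleeding control will be overstated. The timing table shows this is true only for interventions between the grades, and nothing shows that any will occur there. The other is that leaving out the bleeding questions inflates the result. It does not: it loses a direct outcome and a cross-check and leaves the Boezaart comparison unchanged.

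The change is worth making because it is cheap, and because timing not recorded at surgery may not be recoverable later.

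**What to change.** 1. **Procedure CRF:** record any other haemostatic intervention and whether it came before the pre-packing grade, between the grades, or after the post-packing grade.
2. **SAP 7.9.2, Boezaart change:** report the number of subjects in each timing category. Show the change for all subjects, and separately for those with and without an intervention between the grades.
3. **SAP 7.9.2, bleeding questions:** add the Day 0 and Day 14 items as proportions with exact 95% confidence intervals. As a supporting result, also show the Day 0 proportion controlled without any intervention after the pre-packing grade.
4. **Residual bleeding:** reconcile the statement in Protocol 4.1.2 and SAP 4.2 that residual bleeding is noted at the visits with the absence of a bleeding item at Day 30.

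The cost is one timing item on an existing CRF, some SAP wording and slightly more data entry. The bleeding-control figure may come out less favourable. None of this alters how bleeding is managed.

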9.2 Data Collection

Please refer to the Case Report Form Instructions for details regarding directions on completing CRFs, allowable data on CRFs, and source document requirements. **Table 5** shows the schedule on which CRFs are to be completed by designated investigational personnel.

Table 5: Schedule for Completion of CRFs

CRF	Phase of Protocol			
	Enrollment/ Screening	Procedure	Follow Up	Other
Screening/Baseline	X			
Application		X		
Visit 1 / Visit 2			X	
Adverse Event		X*	X*	X*
Device Deficiencies		X*	X*	X*
Study Exit	X*	X*	X*	X*
Protocol Deviation Form	X*	X*	X*	X*

*Adverse Events, Device Deficiencies, Protocol Deviations, and Study Exit CRFs should be completed at any time point in which the corresponding events occur.

9.3 Scheduled Follow-up Visit Windows

After receiving notice of successful implantation/device application, Medtronic will provide the target dates and windows for each subject's visits to the study site if applicable. Should a subject miss a visit or the visit fall outside the pre-specified window, a study deviation must be reported, and the original follow-up schedule maintained for subsequent visits.

Data analyses include follow-up visits, regardless of whether the visit occurs within the window. Therefore, a late visit is preferred over a missed visit but must be accompanied by a deviation report. Follow-up visit windows are listed in **Table 6** and are based on days post-implant.

Table 6: Data collection and study procedure requirements at subject visits

Study Follow-up Visit	Window (Calculated days post-surgery)		
	Window Start (days post-surgery)	Target (days post-surgery)	Window End (days post-surgery)
1. Day 14 (-2, +5)	12	14	19
2. Day 30 (-2, [contact]

9.4 Subject Screening

All subjects that are considered for the study should be screened based on the inclusion/exclusion criteria. The reason for non-eligibility, as determined by the Investigator should also be recorded on appropriate eligibility eCRF. The screening information serves as a method for Medtronic to assess selection bias in the trial and other reasons for subject rejection (e.g., subject with a known shellfish allergy). Additional shellfish allergy criteria questions have been added to determine the potential subjects' eligibility based on their previous exposure risk to shellfish and other organisms containing the tropomyosin protein. If the potential subject is completely naïve to shellfish allergic status the site primary investigator will assess the risk based on responses to screening questions and may either include, exclude or test the subject for shellfish allergy potential.

9.5 Prior and Concomitant Medications/Therapies

Subjects that are immunocompromised and/or are taking immunosuppressive medication are not eligible for this study. There are no other medication/therapy restrictions in the study unless they are investigational and may confound the study results, in which case, prior approval would be needed from Medtronic.

9.6 Subject Consent

Informed consent is defined as a legally effective documented confirmation of a subject's (or their legally authorized/designated representative or guardian) voluntary agreement to participate in a particular study after information has been given and explained to the subject on all aspects of the study that are relevant to the subject's decision to participate. This process includes obtaining an IC form (and where required, a/an Authorization to Use and Disclose Personal Health Information/Research Authorization/other privacy language as required by law) that has been approved by Medtronic and the study IRB/REB (specific study site or central IRB/REB where authorized) and signed and dated by the subject (or their legally authorized/designated representative or guardian). A subject may only consent after information has been given and explained to the subject on all aspects of the clinical investigation that are relevant to the subject's decision to participate. IC may be given by the legally

Medtronic Business Restricted

authorized/designated representative only if a subject is unable to make the decision to participate in a clinical investigation. In such cases, the subject shall also be informed about the clinical investigation within his/her ability to understand.

The template IC will be provided under separate cover. Prior to enrolling subjects, the IC site (and where required the Authorization to Use and Disclose Personal Health Information/Research Authorization/other privacy language as required by law) must be approved by Medtronic and the IRB/REB. The document(s) must be controlled (i.e. versioned and dated) to ensure it is clear which version(s) were approved by the IRB/REB. Any adaptation of the sample IC must be reviewed and approved by Medtronic and the IRB/REB reviewing the application prior to enrolling subjects.

The investigator must notify the subject (or their legally-authorized/designated representative or guardian) of any significant new findings about the study that become available during the course of the study which are pertinent to the safety and well-being of the subject, as this could impact a subject's willingness to participate in the study. If relevant, consent may be requested from subjects to confirm their continued participation.

Prior to initiation of any study-specific procedures, IC must be obtained from the subject (or their legally authorized/designated representative or guardian). Likewise, privacy or health information protection regulation may require subjects to sign additional forms to authorize study sites to submit subject information to the study sponsor. The IC process must be conducted by the principal investigator or an authorized designee, and the IC Form (and where required, Authorization to Use and Disclose Personal Health Information/Research Authorization/other privacy language as required by law) must be given to the subject (or their legally authorized/designated representative or guardian) in a language he/she is able to read and understand. The process of IC must be conducted without using coercion or undue improper influence on or inducement of the subject to participate by the investigator or other study site personnel. The IC process shall not waive or appear to waive subject's legal right. The language used shall be as non-technical as possible and must be understandable to the subject and the impartial witness, where applicable.

The subject must have ample time and opportunity to read and understand the IC form, to inquire about details of the study, and to decide whether or not to participate in the study. All questions about the study should be answered to the satisfaction of the subject.

When the subject decides to participate in the study, the IC must be signed and personally dated by the subject and investigator or authorized designee, as required by the IC, and ensured by the principal investigator or his/her authorized designee.

A copy of the IC (and where required, the Authorization to Use and Disclose Personal Health Information/Research Authorization/other privacy language), signed and dated as required by law, must be provided to the subject and his/her authorized designee.

Medtronic Business Restricted

If the IC is obtained the same day the subject begins participating in study-related procedures, it must be documented in the subject's case history that consent was obtained prior to participation in any study-related procedures. It is best practice for the IC process to be documented in the subject's case history, regardless of circumstance.

In the event the subject or legally designated representative cannot read and/or write, the IC process shall be obtained through a supervised oral process. An independent and impartial witness must be present during this process. The IC and any other information must be read aloud to the prospective subject or his/her legally designated representative. Whenever possible, either the subject or his/her legally designated representative shall sign and personally date the informed consent form. The witness signs and personally dates the IC attesting that the information was accurately explained and that informed consent was freely given.

The original of the signed IC must be filed in the hospital/clinical chart and/or with the subject's study documents.

The IC (and where required, Authorization to Use and Disclose Personal Health Information/Research Authorization/other privacy language as required by law) must be available for monitoring and auditing.

